10.1.3 SAE reporting

To ensure participant safety, every SAE, regardless of causality, occurring after the participant has provided informed consent and until EOS (Day 56) must be reported to Novartis Safety immediately, without undue delay, under no circumstances later than within 24 hours of learning of its occurrence. Detailed instructions regarding the submission process and requirements are to be found in the Investigator folder provided to the study site. Information about all AEs is collected and recorded on the Serious Adverse Event Report Form: all applicable sections of the form must be completed in order to provide a clinically thorough report.

SAEs occurring after the participant has provided informed consent until the time the participant is deemed a Screen Failure must be reported to Novartis.

All follow-up information for the SAE including information on complications, progression of the initial SAE and recurrent episodes must be reported as follow-up to the original episode

within 24 hours of the Investigator receiving the follow-up information. An SAE occurring at a different time interval or otherwise considered completely unrelated to a previously reported one must be reported separately as a new event.

If the SAE is not previously documented in the Investigator's Brochure and is thought to be related to ABO809, a CMO & PS Department associate may urgently require further information from the Investigator for health authority reporting. Novartis may need to issue an Investigator Notification (IN) to inform all Investigators involved in any study with ABO809 that this SAE has been reported.

Suspected Unexpected Serious Adverse Reactions (SUSARs) will be collected and reported to the competent authorities and relevant ethics committees as per national regulatory requirements in participating countries.

If any SAEs are experienced after EOS (i.e. Post-Study Safety Follow-up calls at 6 and 12 months) in which the Investigator considers there is a reasonable possibility thatABO809 caused the event, the event should be recorded, reported, and captured in the Novartis safety database. All such SAEs will be included in an addendum to the CSR and reported to the competent authorities and relevant ethics committees as per national regulatory requirements in participating countries.

10.1.4 Pregnancy reporting

Pregnancies

Women of child-bearing potential, defined as all women physiologically capable of becoming pregnant, are excluded from study unless they are using highly effective methods of contraception while in the study (see Section 5.2). Therefore, pregnancies are not expected during the study.

However, if a female trial participant becomes pregnant, ABO809 must not be administered (if detected before dosing), and the pregnancy consent form should be presented to the trial participant. The participant must be given adequate time to read, review, and sign the pregnancy consent form. This consent form is necessary to allow the Investigator to collect and report information regarding the pregnancy. To ensure participant safety, each pregnancy occurring after signing the informed consent must be reported to Novartis within 24 hours of learning of its occurrence. If the pregnancy is detected between Day 1 and EOS the pregnancy should be followed up to determine outcome, including spontaneous or voluntary termination, details of the birth, and the presence or absence of any birth defects, congenital abnormalities, or maternal and/or newborn complications.

Pregnancy should be recorded and reported by the Investigator to the Novartis Chief Medical Office and Patient Safety (CMO&PS). Pregnancy follow-up should be recorded on the same form and should include an assessment of the possible relationship to the study treatment any pregnancy outcome. Any SAE experienced during pregnancy must be reported.

Pregnancy outcomes should also be collected for the female partners of any males who received ABO809 in this study if the calculated day of conception is between Day 1 and EOS. Consent to report information regarding these pregnancy outcomes should be obtained from the mother.

The newborn conceived between Day1 and EOS will be followed up for a minimum of 1 year after delivery.

10.1.5 Reporting of study treatment errors including misuse/abuse

Medication errors are unintentional errors in the prescribing, dispensing, administration or monitoring of a medicine while under the control of a healthcare professional, participant or consumer (EMA definition).

Misuse refers to situations where the medicinal product is intentionally and inappropriately used not in accordance with the protocol.

Abuse corresponds to the persistent or sporadic, intentional excessive use of a medicinal product, which is accompanied by harmful physical or psychological effects.

Nitazoxanide errors and uses outside of what is foreseen in the protocol will be recorded on the appropriate eCRF irrespective of whether or not associated with an AE/SAE and reported to Novartis Safety only if associated with an SAE. Misuse or abuse will be collected and reported in the safety database irrespective of being associated with an AE/SAE within 24 hours of Investigator's awareness.

Table 10-1 Guidance for capturing the nitazoxanide errors including misuse/abuse

Treatment error type	Document in Dosing eCRF (Yes/No)	Document in AE eCRF	Complete SAE form
Unintentional nitazoxanide error	Yes	Only if associated with an AE	Only if associated with an SAE
Misuse/Abuse	Yes	Yes	Yes, even if not associated with a SAE

For more information on AE and SAE definition and reporting requirements, please see Section 10.1.1 and Section 10.1.2.

10.2 Additional Safety Monitoring

Not applicable

11 Data Collection and Database management

11.1 Data collection

The Investigator or designated staff will enter the data required by the protocol into the Electronic Case Report Forms (eCRF). The eCRFs have been built using fully validated secure web-enabled software that conforms to 21 CFR Part 11 requirements; the Investigator and site staff will not be given access to the EDC system until they have been trained. Automatic validation programs check for data discrepancies in the eCRFs, allow modification and/or verification of the entered data by the investigator or designated staff.

The Investigator/designee is responsible for assuring that the data (recorded on eCRFs) (entered into eCRF) is complete, accurate, and that entry and updates are performed in a timely manner. The Investigator must certify that the data entered are complete and accurate.

Certain data may be captured via other source documentation (such as safety laboratory data report) and then transcribed, uploaded or transferred into the system. This, and any additional data treated in this manner, will be source data verified by the Novartis study monitor per the monitoring plan and the location of source data (i.e., source, paper or a local electronic system) will be documented prior to study start in the Data Quality Plan. The system has the ability to illustrate when a document has been entered from another source. When using an electronic source record as the original point of data capture, there is no additional data entry step for the site for data collected directly into the application; rather, the electronic source record directly populates the study database. Automatic validation programs check for data discrepancies and, by generating appropriate error messages, allow the data to be confirmed or corrected before transfer of the data to Sponsor. Remote monitoring of the original electronic source records will take place, however on-site monitoring inspections will continue to take place in order to review data entry of source documentation directly captured on paper and transcribed into the system, to ensure protocol adherence, to assess site operational capabilities, and to perform other monitoring activities that cannot be performed remotely.

After final database lock, the Investigator will receive copies of the participant data for archiving at the investigational site.

All data should be recorded, handled and stored in a way that allows its accurate reporting, interpretation and verification.

11.2 Database management and quality control

Novartis personnel (or designated CRO) will review the data entered by investigational site staff for completeness and accuracy. Electronic data queries stating the nature of the problem and requesting clarification will be created for discrepancies and missing values and sent to the investigational site via the EDC system. The Investigator or designated site staff are required to respond promptly to queries and to make any necessary changes to the data.

Concomitant treatments and prior medications entered into the database will be coded using the WHO Drug Reference List, which employs the Anatomical Therapeutic Chemical classification system. Medical history/current medical conditions and adverse events will be coded using the Medical dictionary for regulatory activities (MedDRA) terminology.

Once all the necessary actions have been completed and the database has been declared to be complete and accurate, it will be locked and made available for data analysis. Any changes to the database after that time can only be made after written agreement by Novartis development management.

11.3 Site monitoring

Before study initiation, at a site initiation visit or at an Investigator's meeting, a Novartis or delegated CRO representative will review the protocol and data capture requirements (i.e. eSource or eCRFs) with the Investigators and their staff. During the study, Novartis employs several methods of ensuring protocol and GCP compliance and the quality/integrity of the site's data. The Novartis field monitor will visit the site to check the completeness of participant records, the accuracy of data capture / data entry, the adherence to the protocol and to Good Clinical Practice, the progress of enrollment, and to ensure that study treatment is being stored,

Page **71** of **81**

dispensed, and accounted for according to specifications. Key study personnel must be available to assist the field monitor during these visits. Continuous remote monitoring of the site's data may be performed by a centralized Novartis/delegated CRO/CRA organization. Additionally, a central analytics organization may analyze data & identify risks & trends for site operational parameters, and provide reports to Novartis clinical teams to assist with trial oversight.

The Investigator must maintain source documents for each participant in the study, consisting of case and visit notes (hospital or clinic medical records) containing demographic and medical information, laboratory data, electrocardiograms, and the results of any other tests or assessments. All information on eCRFs must be traceable to these source documents in the subject's file. The Investigator must also keep the original informed consent form signed by the participant (a signed copy is given to the participant).

The Investigator must give the Novartis monitor access to all relevant source documents to confirm their consistency with the data capture and/or data entry. Novartis monitoring standards require full verification for the presence of informed consent, adherence to the inclusion/exclusion criteria, documentation of SAEs, and of data that will be used for all primary and secondary objectives. Additional checks of the consistency of the source data with the eCRFs are performed according to the study-specific monitoring plan. No information in source documents about the identity of the participants will be disclosed,

12 Data analysis and statistical methods

The statistical analysis of this study will be performed by Novartis or a designated CRO. Any data analysis carried out independently by the Investigator should be submitted to Novartis before publication or presentation. Procedures for data analysis will be further specified in the Statistical Analysis Plan (SAP). A Clinical Study Report (CSR) will be prepared following the Day 56 visit.

12.1 Analysis sets

For all analysis sets, participants will be analyzed according to the dose of ABO809 (*C. parvum* oocysts, also referred to as "treatment").

The safety analysis set will include all participants that received ABO809.

The PD analysis set includes all participants with available safety, parasitological and clinical data and with no protocol deviations with relevant impact on PD data.

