6.4 Treatment blinding

Treatment will be open to participants, investigator staff, person performing the assessments and the Novartis clinical trial team (CTT).

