2.2 Analysis sets

For all analysis sets, participants will be analyzed according to the dose of ABO809 received (*C. parvum* oocysts, also referred to as "treatment").

The full analysis set (FAS) and safety analysis set (SAF) will be comprised of all participants who took one dose of ABO809 during the treatment period.

The Pharmacodynamic (PD) analysis set includes all participants with available parasitological and clinical data and with no protocol deviations with relevant impact on PD data. Fecal stool samples will also be assessed for other enteric pathogens which may cause diarrheal illness. Any participant with a positive test for these other enteric pathogens will be excluded.

The protocol deviation codes are summarised in Appendix Section 5.6.

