2.4 Analysis supporting primary objective(s) (PD analysis set)

2.4.1 Primary endpoint(s)

The primary endpoint is *Cryptosporidium* infection up to Day 10 (inclusive). This is defined as detection of oocysts

- in at least one fecal sample at \geq 72 hours after ABO809 administration
- or sooner than 72 hours if associated with symptoms suggestive of diarrheal illness, in at least one fecal sample after ABO809 administration.

Fecal stool samples will be assessed for *Cryptosporidium* infection using a commercially available diagnostic EIA test and confirmed by DFA test if the EIA is positive. Tests will be performed at a CLIA certified laboratory. Samples that test negative for *Cryptosporidium* by EIA will be reported as negative for *Cryptosporidium* without confirmation by DFA.

To overcome stool-to-stool and day-to-day oocyst shedding variability, up to 3 consecutive stool specimens, produced about 3-4 hours apart and on the same day will be tested. If at least one of the stool samples is *Cryptosporidium* positive, the participant will be considered infected. Otherwise, the participant will not be considered infected.

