2.4.4 Sensitivity analyses

Not Applicable

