2.5 Analysis supporting secondary objectives

The secondary objectives of this study are to (1) evaluate the incidence and characteristics of diarrheal illness (PD analysis set), (2) to evaluate the time to onset and resolution of *Cryptosporidium* infection (PD analysis set), and (3) to assess the safety and tolerability of ABO809 (Safety analysis set).

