5.6 Rule of exclusion criteria of analysis sets

Table 5-6 Protocol deviations leading to exclusion

	9	
Analysis Set	Criteria that cause subjects to be excluded	
SAF	Not treated with study treatment;	
PD	Not having informed consent; Not treated with study medication;	
	Not meeting entry criteria;	
	No evaluable, parasitological and clinical data;	
	Use of prohibited medication or vaccination during the study;	

6 Reference

Clopper, C. J. and Pearson, E. S. (1934), "The Use of Confidence or Fiducial Limits Illustrated in the Case of the Binomial," *Biometrika*, 26, 404-413.

Collett, D. (1994), Modeling Survival Data in Medical Research, London: Chapman & Hall.

ICH E9(R1) Harmonized Guideline: addendum on estimands and sensitivity analysis in clinical trials to the guideline on statistical principles for clinical trials. Final version on 20 November 2019.

Toxicity Grading Scale for Healthy Adult and Adolescent Volunteers Enrolled in Preventive Vaccine Clinical Trials (2007). Guidance for Industry. U.S. Food and Drug Administration (Internet) Available from: (Accessed 09 July 2021).

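### In the visible plan, infection and illness rates are estimated on the PD set, which can drop dosed participants for events that depend on the outcome, with no all-dosed check

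*Protocol*

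**What the plan says.** **Set definitions.** Protocol 12.1 builds the PD set from participants who have safety, parasitological and clinical data and "with no protocol deviations with relevant impact on PD data". It does not say which set serves the primary analysis. SAP 2.2 drops the requirement for safety data and adds a rule on other enteric pathogens: "Any participant with a positive test for these other enteric pathogens will be excluded". That sentence gives no time limit. SAP Table 5-6 (section 5.6) lists the deviations that remove someone from the PD set, among them "Use of prohibited medication or vaccination during the study".

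**Assignment.** The title of SAP 2.4 is "Analysis supporting primary objective(s) (PD analysis set"), and SAP 2.5 gives the same set to the objective to "evaluate the incidence and characteristics of diarrheal illness (PD analysis set").

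**All-dosed set.** SAP 2.2 states: "The full analysis set (FAS) and safety analysis set (SAF) will be comprised of all participants who took one dose of ABO809". The two sets hold the same people. Under the SAF name they serve demographics, medications and safety. Under the FAS name they appear in no visible analysis.

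**Checks on the primary result.** SAP 2.4.4 and 2.4.5, on sensitivity and supplementary analyses, both read "Not Applicable", and Protocol 12.4.2 says the same of supplementary analysis. For the secondary endpoints, SAP 2.5.5 plans no sensitivity analysis and the content of SAP 2.5.6 is redacted.

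**Context.** Protocol 9.1.1.1 rules out replacement of participants. On blinding, Protocol 6.4 says: "Treatment will be open to participants, investigator staff, person performing the assessments".

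**The concern.** The primary objective is the incidence of infection after ABO809 is given, which reads naturally as a rate per challenged volunteer. SAP 1.2.1 defines no estimand that would narrow it. Later challenge studies will lean on this rate and on the illness rate.

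The PD set is not a neutral subset of those dosed, for three reasons:

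- **Exclusions can follow from illness.** Antidiarrheals are prohibited through Day 28 (Protocol 6.2.2), and people with diarrhea are the likeliest to take them. A footnote to Protocol Table 8-1 has the first diarrheal stool tested for other enteric pathogens. On the visible text, therefore, those tested after dosing are those with diarrhea.
- **Exclusion applies to the whole participant, not to a period.** Someone who completes the Day 10 endpoint and takes a prohibited drug on, say, Day 20 loses an infection result that was already observed and valid.
- **Some judgement remains.** Whether a deviation has relevant impact is decided in an open-label study, where infection and illness are reviewed cohort by cohort (Protocol 6.5.1). Nothing visible requires that decision to be made without knowledge of the outcome.

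One classification is also unclear. SAP Table 5-4 lists paromomycin, alone or with azithromycin, as prohibited. Protocol 6.2.3 and SAP 2.3.4 allow the same drugs as rescue. Whether such use removes a participant from the PD set cannot be determined.

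**Working it through.** **Inputs**

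- n = 30: the approximate ceiling for one dose level group (Protocol 3) and one of the sizes in Protocol 12.8.
- Planning rates: infection 90% (Protocol 12.8.1) and clinical symptoms 70% (Protocol 12.8.2), the latter used here for illness.
- Limit: lower limit of the 1-sided 80% exact interval (Protocol 12.4.1), L(x, n) = 20th percentile of Beta(x, n − x + 1).
- Exclusions: k = 2 or 3. This is an assumption, since the documents give no rate. The extremes are computed first, then a mixed case.

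**Step 1: reproduce the plan's figures.** Take the largest r for which P(X ≥ r) is at least 0.80, then compute L(r, n).

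- Infection, p = 0.90, n = 30: P(X ≥ 26) = 0.8245 and P(X ≥ 27) = 0.6474, so r = 26 and L = 0.7861. The protocol states 78%.
- Illness, p = 0.70, n = 30: P(X ≥ 19) = 0.8407 and P(X ≥ 20) = 0.7304, so r = 19 and L = 0.5399. The protocol states 53%.

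At n = 20 and n = 60 the limits are 0.7414 and 0.8157 for infection, and 0.4809 and 0.5880 for illness. All six agree with the protocol when cut down to whole percent, so the limit formula is the plan's own.

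**Step 2: why the shift is unequal.** Let p = x/n.

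- Removing k non-events changes the rate by x/(n − k) − x/n = +kp/(n − k).
- Removing k events changes it by (x − k)/(n − k) − x/n = −k(1 − p)/(n − k).

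The ratio of the two is p/(1 − p): 9 at p = 0.90 and about 2.3 at p = 0.70. For infection with k = 3 this gives +3(0.9)/27 = +10.0 points against −3(0.1)/27 = −1.1 points.

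**Step 3: rates and 1-sided 80% lower limits**

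| Case | Infection: rate (limit) | Illness: rate (limit) |
|---|---|---|
| All 30 dosed | 27/30 = 90.0% (82.4%) | 21/30 = 70.0% (60.8%) |
| 2 non-events removed | 27/28 = 96.4% (89.7%) | 21/28 = 75.0% (65.6%) |
| 3 non-events removed | 27/27 = 100% (94.2%) | 21/27 = 77.8% (68.3%) |
| 2 events removed | 25/28 = 89.3% (81.2%) | 19/28 = 67.9% (58.2%) |
| 3 events removed | 24/27 = 88.9% (80.5%) | 18/27 = 66.7% (56.8%) |

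Mixed case for infection, removing 2 infected and 1 uninfected: 25/27 = 92.6% (84.8%), a rise of 2.6 points.

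**Step 4: the SAP's interval.** SAP 2.4.2 reports a 2-sided 80% interval, whose lower limit is the 10th percentile of the same Beta distribution. For infection it is 79.1% at 27/30, 86.8% at 27/28, 91.8% at 27/27, 77.7% at 25/28 and 76.9% at 24/27. The levels are lower but the pattern is the same.

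**Step 5: against the planning figure.** With 24/30 = 80.0% infected the 1-sided limit is 71.3%, below the 78% in Protocol 12.8.1. Removing 3 uninfected gives 24/27 = 88.9% with limit 80.5%, above it. The 78% is a planning statement, not a decision threshold, so this shows scale only.

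**The case against.** The other side has several good arguments.

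- **The exclusions are not open-ended.** SAP Table 5-6 lists categories in advance, and only deviations with relevant PD impact count. A reader might infer that the set is free of all deviations, or is picked at will once results are known. The text supports neither. Some judgement remains, and one listed category can follow from illness.
- **The Day 10 window is protected.** Dosing is supervised and everyone is domiciled through Day 10, so unsupervised antidiarrheal use before then is unlikely. This stands, but Table 5-6 covers the whole study, so later use still removes the Day 10 result.
- **The counts are assumed.** All-infected or all-uninfected exclusions are extremes. The triggers most clearly tied to outcome would tend to remove ill participants, for whom the effect on the infection rate is small. The upward shift needs uninfected people to be removed, for example someone with diarrhea from another pathogen and no *Cryptosporidium*.
- **A PD set is defensible for a challenge model.** An all-dosed analysis includes people whom SAP 2.3.3 calls not fully dosed after vomiting, and counts diarrhea with another pathogen as illness. This is why the documents do not support the tempting conclusion that the FAS must replace the PD set as primary.
- **The consequence is limited.** The analysis is descriptive, dose decisions use a separate evaluable-data definition (Protocol 6.5.1), and SAP 2.4.2 lists EIA results by participant. All true, but a listing gives no all-dosed proportion or limit.

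**Conclusion.** The concern holds in a limited form. The visible plan gives the primary infection rate no all-dosed companion, and the set it uses can discard outcomes already observed because of later events related to illness.

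If 2 or 3 of 30 are excluded at the planning rates, infection can rise by 6.4 to 10.0 points (limit up 7.3 to 11.8) but fall by only 0.7 to 1.1 points (limit down 1.2 to 1.9). Illness can rise by 5.0 to 7.8 points or fall by 2.1 to 3.3. A reader might expect shifts of several points in either direction. For infection that is wrong, because the possible movement is mainly upward. Illness moves both ways, unequally. These sizes rest on assumed numbers of exclusions and on those excluded all having the same outcome.

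Nor can one say that the FAS is used for nothing. The identical SAF serves baseline and safety summaries, SAP 2.5.6 is redacted, and SAP 2.11 and 2.12 show no text. An all-dosed illness or interim analysis cannot be ruled out. For the primary endpoint, however, the visible sections state that there is no sensitivity or supplementary analysis.

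**What to change.** Before database lock:

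1. In SAP 2.4.4 or 2.4.5, and in 2.5.5, add infection (Day 10 and Day 28) and illness (Day 10 and Day 28), with their exact limits, on the FAS by dose, beside the PD-set results. Count each participant by observed stool and illness data. SAP 2.4.1 already treats a participant with no positive sample as not infected.
2. List every PD-set exclusion with its reason, its timing and the participant's observed infection and illness outcome.
3. State in SAP 2.2 and Table 5-6 that an excluding event after an endpoint has been met does not remove that observed outcome.
4. Reconcile SAP Table 5-4 with Protocol 6.2.3 and SAP 2.3.4 on paromomycin, so that it is clear whether rescue use leads to exclusion.

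The cost is a second set of simple tables on a population already defined. The all-dosed rate may be slightly less favourable and will include some participants who were not fully dosed. Showing both sets side by side lets the reader judge how much that matters.
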